Brain regions implicated in Autism: Several studies aiming to identify the etiology of autism have indicated involvement of limbic system structures including the amygdala, hippocampus, & the ACC⁴¹⁻⁴³. These limbic structures also show a high affinity for NMDA receptor binding. ACC: is functionally associated with information processing and response to emotional cues and is, therefore, a region of interest in autism. The ACC also has close anatomic connections to the amygdala & participates in emotional regulation. Lesions of ACC are known to cause blunted affect, disinhibition, disabling repetitive behaviors, & impaired social judgment including the inability to interpret social cues⁴⁴. Converging evidence from various investigative modalities suggests abnormalities in the ACC region in individuals with ASD including histopathological changes of increased cell packing density & decreased cell size, smaller in volume, decrease in regional cerebral blood flow, & metabolically less active^{34-35, 38, 39-40} with abnormal functional activity (theory of mind task related & resting state)⁴⁵⁻⁵². MTL: structures, the hippocampus & amvadala, play crucial roles in associative memory & social cognition, respectively, & lesions in the MTL are implicated in social impairments intrinsic to ASD⁵³⁻⁵⁵. Converging evidence of abnormalities in the MTL in ASD comes from various histopathological & imaging studies revealing decreased neuronal size and increased cell density and cytoarchitectural minicolumnar pathology, bilateral decreased volume & hypo-perfusion, and abnormal activation especially of amygdala on face recognition41,45-46,48, 55-65.

II. SPECIFIC AIMS

Primary Aims

Aim 1) To examine the clinical efficacy & tolerability of memantine for the treatment of social impairment in youth with ASD. We will study the short- & long-term clinical effects of memantine in 40 children and adolescents with ASD by conducting a 12-week randomized-controlled trial (RCT).

Aim 2) To examine the effect of memantine therapy on neural function in youth with ASD. We will assess neural response to memantine therapy by measuring spectroscopic

& resting state functional connectivity (RsFc) changes with memantine treatment. We will also assess association of neural & clinical response to memantine therapy.

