Aim 3) To characterize neural functional deficits and/or abnormalities in youth with ASD by comparing ASD subjects to healthy control subjects undergoing the same spectroscopic & RsFc imaging with two scans 12 weeks apart.

III. LENGTH OF STUDY

This study may take up to 20 weeks from enrollment (allowing up to eight weeks to schedule and complete the initial screening process and baseline scan). Once subjects have completed the screening process and baseline characterization, subjects eligible for scanning will complete a baseline scan (for ASD subjects, this scan will be pre-treatment). ASD subjects will then begin the 12-week randomized-controlled trial. All subjects eligible for scanning, including healthy controls, will receive a follow-up scan approximately 12 weeks after the baseline scan. For ASD subjects, this scan will take place between the 10th and 12th week of treatment. All subjects will be taking the study medication at the time of the second brain scan. ASD subjects ineligible for scanning may participate in the 12-week randomized-control phase of the trial only.

IV. SUBJECT SELECTION CRITERIA

A. Inclusion Criteria (all participants)

1. Male & female subjects ages 8-18 years (inclusive).

Participants with ASD

- 3. DSM-5 ASD diagnostic criteria as established by clinical diagnostic interview
- 4. At least moderate severity of social impairment as measured by a total raw score of ≥85 on the parent/guardian-completed Social Responsiveness Scale-Second Edition (SRS-2)⁷¹ and a score of ≥4 on the clinician-administered Clinical Global Impression-Severity scale (CGI-S).

Healthy Control Participants

- 3. Age-, sex-, & IQ-matched with ASD participants.
- No Axis I diagnoses as established by the Kiddie Schedule for Affective Disorders and Schizophrenia—Epidemiological Version (K-SADS-E)⁷⁰ & confirmed by clinical diagnostic interview.
- 5. No significant traits of ASD as screened by SRS-2 (raw score <60).

Exclusion Criteria (all participants)

- 1. IQ ≤70 based on the Wechsler Abbreviated Scale of Intelligence-II (WASI-II) Vocabulary and Matrix Reasoning subtests
- 2. Impaired communicative speech
- 3. Subjects currently treated with the following medications (known to impact glutamate levels):
 - a. Lamotrigine
 - b. Amantadine

- c. N-acetylcysteine
- d. D-cycloserine
- 4. Subjects treated with a psychotropic medication not listed above on a dose that has not been stable for at least 4 weeks prior to study baseline.

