After the 2D-JPRESS dataset is resolved into a series of one-dimensional spectra where each spectrum is modeled and fitted with GAMMA simulated J-resolved basis sets, Glu levels will be derived from the total integral across the J-series. Glu transverse relaxation time (T2) will be obtained from the raw peak vs. TE decay curve fitted with

Levenberg-Marquardt algorithm using an exponential decay function (for Glu T2) convoluted with a polynomial function (for Glu J-coupling) that will be obtained from the GAMMA simulation run with previously measured spectral parameters. Data quality will be assessed by LCModel calculated Full Width Half Maximum (FWHM), Signal to Noise Ratio (SNR) and Cramer-Rao Lower Bounds (CRLB).

The following brain measures will be examined between groups and withinsubject across time (e.g., pre- versus post-treatment and correlations between the measures of brain activity and clinical features):

1) ¹HMRS measures of brain Glu in:

a) ACC

b) MTL

2) measures of resting state functional connectivity of:

- a) dorsal & ventral ACC with prefrontal cortex including VMPFC;
- b) bilateral amygdala with insula & VMPFC;

c) bilateral hippocampus with posterior cingulate cortex.

Pretest-posttest brain activity differences will be analyzed using linear regression models, where treatment group is the primary predictor and pretest measures of brain activity are covariates. A general linear regression model will evaluate the difference between the treatment groups in posttest brain measures while controlling for each subject's pretest measures of brain activity. This approach is equivalent to analyses of covariance (ANCOVA). We will also test if changes in Glu in memantine and placebo (PBO) responders differ from changes in Glu over time in healthy controls (HCs). This requires a three-group comparison: memantine responders vs. PBO responders vs. HCs. We will use a GLM to compare Glu changes from baseline to endpoint. If the direction and magnitude of change among the three groups are the same, there will be no group by time interaction. If the interaction is significant and responders show greater changes compared to HCs, it will indicate that the changes observed in responders are greater than expected from normal changes in Glu activity. We will do follow-up tests to separately test the interactions for each pair of the three groups analyzed.

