We also predict normalization of brain activity measures with memantine treatment. "Normalization" will be defined as having achieved a resting state functional connectivity level that is no more extreme than the 95th percentile of the control distribution. Normalization ratings between the memantine and PBO groups will be compared using a logistic RMs. A significant effect would mean an increased likelihood of normalization in memantine-treated subjects.

To test our hypothesis of a significant association between neural and clinical response and between glutamate and functional connectivity response, we will use endpoint clinical efficacy scores as the dependent variable and change in brain activity measures from baseline to endpoint as the independent variables. For our exploratory hypothesis examining neural biomarkers of response to memantine therapy, we will use a GLM with endpoint clinical efficacy scores as the dependent variable, baseline brain activity measures as the independent variables, and baseline clinical scores as a covariate.

Resting state data will be analyzed using a seed driven approach with custom software (Conn)⁸⁸. Data will be slice time corrected, realigned, coregistered, normalized, and spatially smoothed as necessary. Physiological & other spurious sources of noise

will be estimated using the CompCor method, and removed together with movementrelated covariates. The residual BOLD time-series will be band-pass filtered over a lowfrequency window of interest (0.009Hz<f<0.08Hz). Correlation maps will be produced by extracting the residual BOLD time course from bilateral anatomically defined amygdala (WFU_Pickatlas) seed regions, and computing Pearson's correlation coefficients between that time course and the time course of all other voxels. Correlation coefficients will be converted to normally distributed scores using Fisher's transform to allow for second-level General Linear Model analyses. Between group differences will be calculated for each ROI.

Power Considerations

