Spectroscopic: For our preliminary data from 7 ASD and 7 HC subjects, our significant finding (paired t-test, p =0.01) of 31% higher Glu levels in the ACC of ASD subjects compared to HCs was determined to have a large effect size of d=1.20 with an associated power= 0.55. Left MTL data produced an effect size d=1.03 with power = 0.43. Right MTL data produced an effect size d=1.15 with power =0.51. Assuming we observe the same sampling variability in the proposed study, we have greater than 90% power with a large effect size of d=1.10 to detect a 15% decrease in Glu in the ASD group with treatment.

Functional: In our preliminary studies (ASD: N=17; HC: N=16) of resting state functional connectivity with the bilateral amygdalae seeds, we found significant hyperconnectivity of the ASD group compared to the HC group (e.g., with the insula, p<0.0001 FWE cluster level corrected), and based on the preliminary data, power will be at 95% to detect between-group differences between the proposed ASD (N=40) and HC groups (N=20).

VII. RISKS AND DISCOMFORTS

Risks of Taking Memantine:

The most frequently observed adverse reactions with memantine are dizziness, confusion, headache, constipation, hypertension, cough, pain, hallucinations, somnolence, vomiting, dyspnea, and fatigue. Serious adverse reactions include Stevens-Johnson syndrome and seizures. All participants will be closely monitored for serious adverse reactions and drug-drug interactions with their ongoing concomitant medications. All serious unexpected adverse experiences of a research subject will be reported to the Partners Human Research Committee.

Problems and side effects not listed above and not known at this time could occur. Subjects will be told of any changes in the way the study will be done and any newly discovered risks to which they may be exposed.

Risks of Blood Draws:

When blood is drawn, some discomfort may be associated with it at the time of the blood draw. Bruising and/or bleeding at the needle site may occur. Occasionally a person feels faint. Rarely, an infection may develop. If an infection does occur, it can be treated. A topical anesthetic cream (Topicaine, EMLA, or ELA-MAX) will be applied to numb the skin where blood will be drawn if subjects prefer.

Risks of ¹HMRS:

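### Primary Aim 2 rests on five listed brain measures (seven when unpacked) with no lead measure, alpha or multiplicity rule; at an assumed 5% per test, the chance of a false-positive drug effect is about 15% to 30%

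*Combined protocol and SAP*

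**What the plan says.** Section II (Specific Aims) places three aims under the Primary Aims heading. Two concern imaging: "Aim 2) To examine the effect of memantine therapy on neural function in youth with ASD" and "Aim 3) To characterize neural functional deficits and/or abnormalities in youth with ASD by comparing ASD subjects to healthy control subjects".

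Section VI (Biostatistical Analysis), Neuroimaging Data Analysis, states "The following brain measures will be examined between groups" and over time within subjects. It then lists five lettered items:

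- Glu in the ACC
- Glu in the MTL
- dorsal and ventral ACC connectivity with prefrontal cortex
- bilateral amygdala connectivity with insula and ventromedial prefrontal cortex (VMPFC)
- bilateral hippocampus connectivity with posterior cingulate

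The treatment comparison is an ANCOVA: the post-treatment measure regressed on arm and the pre-treatment measure. The section adds a three-group Glu comparison of responders and controls with pairwise follow-up, a normalization analysis, and association analyses. Of the normalization analysis it says "A significant effect would mean an increased likelihood of normalization in memantine-treated subjects". Group differences are to be computed separately for each region of interest. The word exploratory is attached to one hypothesis only, on baseline biomarkers of response.

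Power Considerations gives pilot Glu results for 7 ASD and 7 control subjects. ACC is called significant (d=1.20, power 0.55). For the MTL it reports "Left MTL data produced an effect size d=1.03 with power = 0.43" and "Right MTL data produced an effect size d=1.15 with power =0.51". For the trial it claims more than 90% power at d=1.10 for a 15% fall in Glu with treatment. The only multiplicity wording in the document is a cluster-level family-wise correction, which describes the pilot connectivity result.

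**The concern.** A primary aim should say which result would answer it. Here several measures serve Aim 2 on equal footing, and nothing limits the overall error rate across them. If memantine changed none of them, a reader of the trial report could still be shown one significant region out of five or seven as evidence of a neural effect, with no pre-stated basis for discounting it. The stated Glu power fits a single unadjusted test, while the analysis section runs several.

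**Working it through.** **Inputs.** Five lettered measures (Neuroimaging Data Analysis). 40 randomized ASD subjects at 1:1, so 20 per arm (sections V and VII). d=1.10 and the pilot figures (Power Considerations). Alpha is not stated.

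**Step 1: which alpha do the plan's own figures imply?** Power of a two-sided, two-sample t test at 0.05, with noncentrality d × √(n₁n₂/(n₁+n₂)):

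| Test | n per group | d | Computed | Stated |
|---|---|---|---|---|
| ACC pilot | 7 | 1.20 | 0.541 | 0.55 |
| Left MTL pilot | 7 | 1.03 | 0.426 | 0.43 |
| Right MTL pilot | 7 | 1.15 | 0.507 | 0.51 |
| Planned Glu test | 20 | 1.10 | 0.924 | >90% |

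A one-sided test (0.68, 0.57, 0.65) and a paired test (0.75, 0.63, 0.72) do not fit the three pilot values, although the text calls the pilot test paired. An unadjusted two-sided 0.05 is therefore a reasonable assumption. It is still an assumption. The planned-test line is consistent with a comparison of 20 v 20, but the text does not say that this is the comparison meant.

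**Step 2: how many measures?** The list has five items. Counting dorsal and ventral ACC apart adds one, and counting amygdala-insula and amygdala-VMPFC apart adds another: 5 + 1 + 1 = 7. Counting left and right MTL apart, as Power Considerations does, gives 8.

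**Step 3: chance of at least one false positive in Aim 2.** One memantine v placebo test per measure, no true effect on any. If the tests are independent the chance is 1 − 0.95ᵏ:

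- k=5: 1 − 0.774 = 22.6%
- k=7: 1 − 0.698 = 30.2%
- k=8: 1 − 0.663 = 33.7%

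For correlated tests, by simulation of k two-sided normal tests with one common correlation (400,000 draws):

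| Correlation | k=5 | k=7 |
|---|---|---|
| 0.3 | 21.0% | 27.2% |
| 0.4 | 19.7% | 25.1% |
| 0.5 | 18.3% | 23.0% |
| 0.7 | 14.9% | 17.9% |

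The documents give no correlation between measures, so the range is shown rather than one value. The responder, normalization and association analyses are not counted.

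**Step 4: what would adjustment cost?** Power at d=1.10 with 20 scanned per arm, as an illustration:

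- unadjusted 0.05: 92%
- first Holm step over four other measures (0.05/4 = 0.0125): 80%
- first Holm step over six other measures (0.05/6 = 0.0083): 75%
- Bonferroni over all seven (0.05/7 = 0.0071): 73%

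**Step 5: why the gate matters.** If ACC Glu is tested at 5% and the rest by Holm at a separate 5% regardless of the first result, overall error can reach about 1 − 0.95² = 9.75%. Testing the rest only after ACC Glu succeeds keeps it at 5%.

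**The case against.** The strongest reply has four parts.

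**The plan sets no rule that any one significant region counts as success.** This stands. The aims are to examine and to characterize, and clinical efficacy is judged on CGI-I and SRS-2. A reader might infer that every significant measure is declared a finding, but the documents attach explicit interpretations only to the responder-control Glu interaction and to normalization. Neither is among the tests counted above. The gap is that nothing states how several results on a primary aim will be read together.

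**Uncorrected testing is inferred from silence.** This stands in part. Connectivity is analysed as seed-based maps, and the pilot amygdala result carried a cluster-level correction, so similar correction within a map may be intended. Such a correction works within one seed's map. It would not cover several seeds plus the Glu voxels.

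**Seven is not the plan's count.** This stands. The plan lists five, and seven is one reasonable unpacking, so a reader should not take seven as a minimum.

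**The pilot does not single out one measure.** This also stands. Amygdala-insula hyperconnectivity was reported at p<0.0001, corrected, in 17 ASD and 16 control subjects. ACC Glu rests on 7 and 7 at p=0.01, and its d is close to that of the right MTL. ACC Glu is nevertheless a sound lead for the drug comparison. It is the region that the pilot calls significant, the background reports raised Glu there and no change in the MTL, and a fall in Glu is the only treatment effect with a power statement. The 95% connectivity power concerns ASD v controls, not the drug.

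**Conclusion.** The concern holds for Aim 2. Five listed measures serve a primary aim with no lead, alpha or multiplicity rule. The chance of at least one false-positive drug effect is about 23% (five) to 30% (seven) if tests are independent, and about 15% to 18% at correlation 0.7. This rests on an assumed two-sided 0.05 per test, one test per measure, and no true drug effect on any measure. Every value in this range is roughly three to six times 5%, but a false positive remains less likely than not.

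A reader might extend the rate to Aim 3, or pool both aims into 14 tests and reach 51%. The documents do not support that. The pilot reports ASD-control differences in ACC Glu and amygdala connectivity, so a null on every measure is not the plan's own scenario for Aim 3.

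This is an inexpensive improvement to the plan. It does not affect the clinical efficacy analysis.

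**What to change.** In Neuroimaging Data Analysis, state that for Aim 2 the memantine v placebo ANCOVA on ACC Glu is the single confirmatory imaging test, at two-sided 5%. For the other listed measures choose one of two routes:

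- write out the list with compound items resolved, and test them by Holm only if ACC Glu is significant; or
- label them exploratory and report estimates with confidence intervals.

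Label the responder, normalization and association analyses exploratory in either case. Say whether cluster-level correction applies within each seed's map. This change does not supply a lead test for Aim 3.

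The cost is SAP wording. ACC Glu keeps its 92% power at d=1.10 if 20 per arm are scanned. Subjects who cannot be scanned may still enter the trial, so the scanned number, and with it the power, may be lower. Under the first route the other measures have about 80% (four others) or 75% (six others) power at the first Holm step, and only once the gate is passed. If they were independent of ACC Glu, the chance of passing both would be 0.924 × 0.799 = 74% or 0.924 × 0.752 = 69%. Under the second route they carry no confirmatory claim.

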Dose Titration Phase (Weeks 1-4): Study medication will be initiated at 2.5 mg/day, will be raised to 5 mg/day on day 4, and will be gradually up-titrated by 5 mg/week to a maximum dose of 20 mg/day. Titration of the study medication will be guided by the (following) forced titration schedule with an option for slower titration or holding at lower dose per clinician judgment. Memantine will be administered in twice daily divided dosages with a total daily dose of \geq 2.5 mg/day.

Study Medication Dosing: Study medication (memantine/placebo) will be titrated to the maximum daily dose during the first 4 weeks of the trial (dose titration phase). Subjects will follow the following forced titration schedule until Week 4 when subjects will be maintained on maximum achieved dose until the end of the trial (dose maintenance phase; Weeks 5-12). During the dose maintenance phase, there will be a one-time option to decrease the dose of the study medication.

Mema	antine Forced	Titration Schedule
Visit	Day	Maximum Total Dose Prescribed (mg/day)
0	1	2.5
	5	5
1	8	10
2	15	15
3	22	20
4	28	Maintained on maximum achieved dose

Primary Outcome Measure of Efficacy: Clinician-rated CGI-Improvement (CGI-I) subscale and the parent-rated SRS-2. Treatment responders will be defined as those who demonstrated improvement of ≥25% on the SRS-2 total raw score *and* a score of 2 or 1 on the CGI-I subscale ("much" or "very much improved").

Secondary Outcome Measures of Efficacy: As with other psychotropic treatment outcomes in this population⁷², response to memantine may not be uniform for all domains of ASD. The response differential will be examined by assessing change in the severity of the subscales of the SRS-2 representing core domains of ASD, change on the ABC-SW subscale, and change on the MGH-ASD-RS (clinician- and informant-rated). The CY-BOCS-PDD⁷³⁻⁷⁴ will be administered to assess change with treatment in the ritualistic behaviors associated with ASD. Change with treatment in the level of adaptive functioning will be assessed by the CBCL. Change in the level of global functioning will be assessed by the parent/guardian-rated SAICA. Considering that features of ADHD, anxiety, & depression are frequently associated with ASD⁴ & there is evidence of memantine's effectiveness in treating ADHD in adults, these symptoms will be assessed by administering the clinician-rated ADHD-SCL, CDRS-R⁷⁹, & CASI-Anx⁸⁰.

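### The added three-group glutamate test compares outcome-selected responders with unselected controls, so selection alone can look like more than normal change

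*Combined protocol and SAP*

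**What the plan says.** Under Neuroimaging Data Analysis (Section VI, Biostatistical Analysis), the lead analysis keeps the randomised groups: "A general linear regression model will evaluate the difference between the treatment groups in posttest brain measures while controlling for each subject's pretest measures". The plan then adds a second glutamate question: "This requires a three-group comparison: memantine responders vs. PBO responders vs. HCs". The method is brief: "We will use a GLM to compare Glu changes from baseline to endpoint". Of a significant interaction with larger change in responders than in controls, the plan says that "it will indicate that the changes observed in responders are greater than expected from normal changes in Glu activity". It adds: "We will do follow-up tests to separately test the interactions for each pair of the three groups analyzed".

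Response is defined in Section VII, under Primary Outcome Measure of Efficacy: "Treatment responders will be defined as those who demonstrated improvement of ≥25% on the SRS-2 total raw score", together with a CGI-I score of 1 or 2. Both components are measured after randomisation. No selection is described for the controls. For this test the plan gives no non-responder comparison, no exploratory label, and no power or expected group size.

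A later paragraph of the imaging section announces a related analysis: "To test our hypothesis of a significant association between neural and clinical response".

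**The concern.** Two of the three groups are chosen because they improved clinically; the third is not chosen on anything measured during follow-up. Such a comparison is balanced only if Glu change is unrelated to clinical change. If the two are related through anything other than the drug, such as maturation, placebo response or a shared time trend, the responders come from one side of the distribution of Glu change and the controls from all of it. The test can then reject although the full ASD and control distributions of change are identical, and the plan would report the responders as exceeding normal change.

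At stake is the interpretation of one mechanistic result. The randomised ANCOVA does not fill the gap, because it compares the treatment groups only. As written, the plan has no unselected comparison of each arm's Glu change with normal change over the same interval, although controls are scanned twice.

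**Working it through.** **Inputs from the documents.** 40 ASD subjects randomised 1:1, so 20 per arm, and 20 controls (Sections V and VII). Fewer ASD subjects may be scanned, because those with MR contraindications may join the drug trial only (Section IV).

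**Assumptions.** The documents give neither a response rate nor a correlation ρ between Glu change and clinical change, so both are varied. Tests are two-sided at 5%, which is also assumed.

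**1. The plan's own power figures.** These reproduce with a two-sample noncentral t, noncentrality d·√(n₁n₂/(n₁+n₂)).
- 7 v 7: the factor is √(49/14) = 1.871. Power is 0.541 at d = 1.20 (stated 0.55), 0.426 at d = 1.03 (stated 0.43) and 0.507 at d = 1.15 (stated 0.51).
- 20 v 20 at d = 1.10: noncentrality 1.10 × √(400/40) = 3.48, power 0.924 (stated as above 90%).

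None of these figures refers to responder subsets.

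**2. Shift caused by selection alone.** Let Glu change be standard normal in every group, with no drug effect and no ASD-control difference. Let response mean that a latent improvement, correlated ρ with Glu change, passes a cut-off reached by a proportion p. The expected Glu change in responders is ρ·φ(z)/p.
- p = 0.50: φ(0)/0.50 = 0.399/0.50 = 0.798, so 0.24 SD at ρ = 0.3 and 0.40 SD at ρ = 0.5.
- p = 0.25: φ(0.674)/0.25 = 0.318/0.25 = 1.271, so 0.38 SD and 0.64 SD.

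**3. Rejection rate of the three-group F test.** Simulation of the model in step 2 with 20 per arm and 20 controls. The 50%/25% row used 6,000 trials per setting. The other rows used 4,000, testing only trials with at least 2 responders in each arm.

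| Response, memantine/placebo | ρ = 0 | ρ = 0.3 | ρ = 0.5 |
|---|---|---|---|
| 50%/25% | 4.9% | 10.8% | 22.0% |
| 30%/30% | 4.5% | 11.7% | 24.4% |
| 50%/50% | 4.7% | 9.6% | 17.8% |
| 50%/30% | 5.4% | 10.7% | 21.7% |
| 60%/20% | 4.9% | 10.3% | 20.4% |

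A separate run of the 50%/25% setting gave 4.9%, 9.4% and 22.4%, hence about 5%, 10% and 22%. With 15 scanned per arm the rates are 5.4%, 9.0% and 19.1%.

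**4. Where the excess lies.** At 30%/30%, memantine responders v controls rejects 10.8% at ρ = 0.3 and 20.5% at ρ = 0.5, while memantine v placebo responders stays at 4.9% for both. At 50%/25%, memantine v placebo responders rejects 5.1%, 5.7% and 6.7% at ρ = 0, 0.3 and 0.5. Only a wide gap in response moves it further: at 60%/20% it reaches 6.7% and 9.9% at ρ = 0.3 and 0.5.

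**5. The same F test on all subjects by randomised arm plus controls.** Rejection is 5.1% for the three groups and 5.0% for memantine v placebo (20,000 trials). No selection takes place, so ρ does not enter.

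**6. Size of the responder subsets.** At 50% and 25% of 20, the responder groups average 10 and 5. Power for 10 v 5 is 0.39 at d = 1.0 and 0.46 at d = 1.10; for 20 v 20 it is 0.87 and 0.92. For responders v 20 controls at d = 1.10, it is 0.78 with 10 responders and 0.62 with 6.

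**The case against.** The strongest reply is that the extra rejections are not errors for the question asked. In the simulated scenario the mean Glu change of responders really does differ from that of controls, so the 10% and 22% are power for a true difference in means. They are type I error only for a drug hypothesis, which this test is not said to address. That is correct as far as the difference in means goes. It does not rescue the stated interpretation. Controls selected on a measure equally correlated with their Glu change would show the same shift, so these responders are one side of the normal distribution of change and do not exceed it.

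Three further replies stand, and they limit the point:

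- A reader might infer that the plan abandons the randomised comparison or offers this test as proof of a memantine effect. It does neither. The ANCOVA by treatment group comes first and is untouched, and the responder test is an addition with a narrower stated reading.
- A reader might infer that selection favours memantine. The contrast most open to that reading, memantine v placebo responders, is only slightly affected. At 50%/25%, rejections showing the larger improvement-linked change in memantine responders fall from 2.5% to 1.2% to 0.8% as ρ goes from 0 to 0.3 to 0.5.
- A reader might infer that the plan itself predicts a drug-independent correlation. It hypothesises an association between neural and clinical response, and Aim 2 ties that to memantine therapy. The correlation in both arms without a drug effect is an assumption here; at ρ = 0 nothing is inflated.

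Finally, the all-subject comparison answers a different question from the responder one, and ASD v control is not randomised either. Both points are accepted and carried into the fix.

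**Conclusion.** The point holds in a limited form. Because responders are selected on outcome and controls are not, a significant three-group result cannot bear the reading that responders changed more than normal. With 20 scanned per group, 50% v 25% response and no drug effect on Glu, the omnibus test rejects about 10% of the time at ρ = 0.3 and about 22% at ρ = 0.5, against about 5% at ρ = 0 or when subjects are grouped by randomised arm. These figures rest on assumed response rates, assumed correlations and identically distributed Glu change in ASD subjects and controls.

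The excess is mainly in responders v controls. Memantine v placebo responders is little distorted (about 5 to 7% at 50%/25%), but it is non-randomised and small. The documents do not support a wider conclusion: the randomised ANCOVA and the clinical analyses stand as planned. This is a cheap improvement to a secondary mechanistic analysis.

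**What to change.** In Neuroimaging Data Analysis, make the comparison with normal change a three-group Glu-change model on all scanned subjects by randomised arm: memantine, placebo and healthy controls. State that memantine v placebo is the randomised contrast in that model. State also that each ASD arm v controls is not randomised, so differences in baseline level, regression to the mean or development could separate them without any drug effect.

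Keep the responder analysis, labelled exploratory or descriptive, with the non-responders of each arm shown alongside and the group sizes reported. Replace the current interpretation with a statement that a responder-control difference will not be read as abnormal change or as a memantine effect.

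The cost is analysis-plan wording only: no new subjects, visits or scans, since controls already have two. The downside is that the all-subject contrast dilutes an effect confined to responders. Showing responders and non-responders side by side keeps such a pattern visible.
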